Figure 1. Changes in stress reactivity (left panel) and weekly measures of stress/anxiety, alcohol craving, depressive symptoms, and alcohol consumption (right panel).

Overall Study Design. To accomplish the project aims, we will utilize a double-blind, mixed-model design with a between-groups factor of dose (pioglitazone vs. placebo) and a within-subjects factor of time. We will utilize urn-randomization based on gender and severity of alcohol use (AUDIT). A summary of the study timeline, procedures, and assessments is shown in **Table 1** below.

Table 1. Outline of Study Timeline, Procedures, and Assessments

Study Week	0	1	2	3	4	5	6	7	8
Procedures and Assessments	IRB	NU	BE						
Consent and Baseline Screening	IRB	APP	OVAL						

SCID, ASI, KMSK, TLFB, CIWAA, AUDIT	X								
Receive Study Medication (Pioglitazone or Placebo)	X	X	X	X	X	X	X	X	X
Assess Medication Compliance and Adverse Events		X	X	X	X	X	X	X	X
Brief Counseling	X	X	X	X	X	X	X	X	X
Human Laboratory Assessments (Specific Aim 1)									
Stress-Reactivity Assessment (Salivary Cortisol, HR, BP, self-report)	X				X				X
Alcohol craving (self-report, brief alcohol demand)	X				X				X
Weekly Assessments (Specific Aim 2)									
Alcohol Use and Craving (TLFB, BrAC, ETG, PACS, DMQ-R)	X	X	X	X	X	X	X	X	X
Stress and Anxiety (HAM-A, PSS, PCL-5)	X	X	X	X	X	X	X	X	X
Delay Discounting, Alcohol Demand (purchasing task)	X				X		X	X	X

SCID - Structured Clinical Interview for DSM-5, **ASI** - Addiction Severity Index⁶⁵; **KMSK** - Kreek-McHugh-Schluger-Kellogg scale⁶⁶; **TLFB** - Timeline Followback⁶⁷; **CIWAA** - Clinical Institute Withdrawal Assessment for Alcohol⁶⁸; **AUDIT** – Alcohol Use Identification Test⁶⁹; **BrAC** – Breath Alcohol Concentration; **ETG** – Ethyl Glucuronide; **PACS** – Pennsylvania Alcohol Craving Scale⁷⁰; **DMQ-R** – Drinking Motives Questionnaire Revised^{1,2}. **HR** – Heart Rate; **BP** – Blood Pressure; **HAM-A** – Hamilton Anxiety Rating Scale⁷¹; **PSS** – Perceived Stress Scale⁷²; **PCL-5** - PTSD Checklist for DSM-5⁷³.

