Brief Counseling. At baseline, all participants will receive the NIAAA booklet "Rethinking Drinking: Alcohol and Your Health" providing research-based information related to alcohol use (RethinkingDrinking.niaaa.nih.gov). Study therapists will go over the booklet with the participant at the initial visit and at subsequent weekly visits using motivational interviewing techniques. At each visit, participants will also be assessed for recent alcohol use (self-report, ETG, BrAC), alcohol craving (PACS), and stress/anxiety (HAM-A, PSS). At the end of the study, referrals to local alcohol treatment services will be provided as needed.

Participant Payment & Compensation. Participants will receive \$50 for completing the baseline screening, \$25/visit for attending study visits (9 visits), \$25/assessment for completing stress reactivity

Table 2. Time Course for Assessing Stress-Induced Relapse Risk

Time (pm)	Study Procedures
3:00	Assess Craving, BAAD, Stress, Cortisol, HR, BP
3:15	Cold Pressor Task
3:20	Assess Craving, BAAD, Stress, HR, BP
3:45	Assess Craving, BAAD, Stress, Cortisol, HR, BP

assessments (3 assessments), \$10/week for medication compliance (8 weeks), and \$100 for completing the study (\$530 total). Participants will also receive \$5 compensation for busfare/parking at each study visit.

DATA ANALYTIC STRATEGY

Descriptive Statistics & Confounding Variables Descriptive statistics will evaluate measures of central tendency (continuous) and frequencies (categorical) for study-related variables. General variable relationships will be evaluated using correlation analyses. Preliminary analyses will inspect relationships between sample characteristics (e.g., demographics), predictor variables (e.g., inflammatory markers), and specified outcome variables (e.g., resilience measures) via traditional statistical tests (e.g., chi-square, Mann-Whitney-Wilcoxon, Kruskal-Wallis, and *t*-tests). Sample characteristic variables demonstrating a relationship with both the predictor and outcome variables in a given model will meet criteria as a potential confounder^{104,105} and included as a covariate in such models for hypothesis testing and explored as potential moderators of treatment group effects on experimental outcomes.

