Missingness & Multiple Comparisons Missing data will be addressed via maximum likelihood, explicit modeling of missingness, and/or imputation where appropriate. Each approach is robust to ignorable missingness (i.e. MCAR and MAR). Sensitivity analyses will permit evaluation of the robustness of findings to missing data assumptions. While Bayesian analyses are not influenced by traditional concerns of multiplicity, for the frequentist analyses, all primary outcome variables (those specified by name in the hypothesis statements below) will be evaluated at the $\alpha = 0.05$ statistical significance level. Secondary analyses will examine additional predictor and outcome variables (e.g., other inflammatory markers collected by assays); these and any otherwise *post hoc* analyses will employ false discovery rate (FDR) to control for Type I error.

Specific Analyses

Specific Aim 1: To examine the effects of pioglitazone on stress-induced relapse risk in a laboratory model. **Hypothesis 1a:** Participants receiving pioglitazone will show decreased stress reactivity (heart rate, blood pressure, salivary cortisol) compared to those receiving placebo. **Hypothesis 1b:** Participants receiving pioglitazone will show decreased alcohol craving (subjective, alcohol demand) compared to those receiving placebo.

For hypothesis 1a, GLMM will model each stress reactivity outcomes (primary: heart rate, blood pressure, and salivary cortisol) as a function of the main effects and higher-order interactions between time (baseline to Week 8), treatment (pioglitazone vs. placebo), and CPT measurement point (pre-CPT vs. post-CPT).

Follow-up analyses will examine lower-order interactions longitudinally as well as cross-sectional changes from pre- to post-CPT at each time point. Variable relationships and analyses for hypothesis 1b will follow the patterns stated above for Hypothesis 1a, with craving in place of stress reactivity.

Specific Aim 2: To examine the effects of pioglitazone on drinking, stress/anxiety, and alcohol craving in the natural environment. **Hypothesis 2a:** Participants receiving pioglitazone will show greater reductions in weekly psychometric measures of stress/anxiety measures: PSS and

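### Potential moderators of the treatment effect are chosen by a confounder screen, which does not test effect modification and which a baseline characteristic can pass in the primary models only by chance imbalance

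*Combined protocol and SAP*

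**What the plan says.** All references are to the combined protocol and SAP.

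- **Entry rule** (Data Analytic Strategy, Descriptive Statistics & Confounding Variables): "Sample characteristic variables demonstrating a relationship with both the predictor and outcome variables in a given model will meet criteria as a potential confounder". The same sentence says that these variables are then "included as a covariate in such models for hypothesis testing and explored as potential moderators of treatment group effects on experimental outcomes". One gate serves both purposes.
- **Screening tests** (same paragraph): relationships are inspected "via traditional statistical tests (e.g., chi-square, Mann-Whitney-Wilcoxon, Kruskal-Wallis, and" *t*-tests), alongside correlations. All are marginal tests. No interaction test is listed and no screening significance level is given.
- **Significance level** (Missingness & Multiple Comparisons): primary outcomes "will be evaluated at the $\alpha = 0.05$ statistical significance level". This is not said of the screen. Secondary and post hoc analyses are allowed under FDR control.
- **Models** (Specific Analyses): Aim 1 uses treatment, time and cold-pressor measurement point with their interactions. Aim 2 uses treatment, time and their interaction.
- **Allocation** (Overall Study Design): urn randomisation on gender and AUDIT.

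The Descriptive Statistics paragraph is the only text on moderators, and no moderator is named anywhere.

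**The concern.** A moderator is a characteristic across which the treatment effect varies. The matching null hypothesis is that there is no treatment-by-characteristic interaction. The written gate asks two other questions: does the characteristic differ between arms, and is it associated with the outcome? Neither involves the interaction. In a randomised comparison the answer to the first is yes only by chance.

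The planned moderator route would therefore pass over nearly all real moderators and pick up whichever prognostic variables happened to be imbalanced. Gender and AUDIT, which the design treats as important enough to balance, would be the least likely to be examined.

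The question has some interest here. Participants may enter on any one of HAM-A, PSS or the coping items of the DMQ-R, so these characteristics will vary within the sample. The Specific Aims section describes the project as groundwork for later R01 studies.

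**Working it through.** **No stated figure.** The documents give no operating characteristic for the screen, so there is nothing to reproduce. The check is a bound, then simulation.

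**Step 1: the bound.** Let A be the event that the characteristic is related to the predictor, and B that it is related to the outcome. A fixed baseline characteristic cannot be related to time or cold-pressor point, so in these models A means related to arm. Then

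P(admitted) = P(A and B) ≤ P(A) = screening α.

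The last equality follows from randomisation. The bound applies per characteristic. It does not grow with the number of outcomes, because the association with arm is the same in every model.

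**Step 2: does the gate respond to moderation?** Setting: 25 per arm (the completer target under Participants), standard normal characteristic x, arm t coded 0/1, unit residual SD, y = b_x·x + b_int·t·x + e, 4,000 trials per row. The gate is a t-test of x by arm and a Pearson x–y correlation, both at p < 0.05 (an assumed level). The effect sizes are also assumptions. The slope of y on x averaged over arms is b_x + b_int/2.

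| b_x | b_int | Average slope | Admitted by gate |
|---|---|---|---|
| 0 | 0 | 0 | 0.2% |
| −0.4 | 0.8 | 0 | 0.4% |
| 0 | 0.5 | 0.25 | 2.0% |
| 0.3 | 0 | 0.30 | 2.4% |
| 0 | 0.8 | 0.40 | 3.7% |
| 0.5 | 0 | 0.50 | 4.2% |
| 0.3 | 0.5 | 0.55 | 4.4% |
| 0.3 | 0.8 | 0.70 | 5.0% |

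Admission rises with the average slope, that is, with prognostic strength, and levels off at α. It does not follow the interaction: a purely prognostic variable (0.5, 0) is admitted more often than a strong crossover moderator (−0.4, 0.8).

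**Step 3: other screening levels.** The level is not stated, so a range is needed. All rows are at 25 per arm. The interaction is 0.8 SD in the first row and 1.0 SD in the others. The ranges run over the assumed main effects of the characteristic.

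| Characteristic | α = 0.05 | α = 0.10 | α = 0.20 |
|---|---|---|---|
| Continuous, interaction 0.8 | 0.3–5.0% | 1.1–10.1% | 4.5–19.8% |
| Continuous, interaction 1.0 | 0.5–4.7% | 1.7–10.1% | 5.4–19.2% |
| Binary 50/50, no urn | 0.2–6.0% | 0.9–10.8% | 3.4–18.9% |
| Binary 50/50, urn-balanced | 0.0–0.15% | 0.05–0.7% | 0.55–3.3% |

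The 6.0% reflects the uncorrected chi-square, which runs slightly above nominal size at this sample size; the cap is the test's actual size. The urn row assumes a UD(1,1) urn within the factor's strata. It stands for a factor such as gender. For AUDIT the reduction depends on how the urn categorises the score, which is not given.

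**Step 4: what a direct test could do.** In the Step 2 model, the interaction test at 0.05 has power of 37–39% for b_int = 0.5 and 74–75% for b_int = 0.8. Its rejection rate with no interaction is 5.1–5.6%. An interaction of 0.8 means the treatment effect differs by 2 × 0.8 = 1.6 SD between people one SD above and one SD below the mean, which is large. These figures are probabilities of detection and the gate figures are probabilities of being examined, so the two should not be subtracted.

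**Step 5: number of tests under a direct approach.** The hypotheses name about ten outcomes: heart rate, blood pressure and cortisol (3); subjective craving and alcohol demand (2); PSS and HAM-A (2); PACS (1); heavy drinking days and drinks/day (2). Five moderators × 10 outcomes = 50 interaction tests.

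**The case against.** **The screening level is not 0.05 by the document's own words.** This stands. A reader might infer that a true moderator is examined at most 5% of the time. The text supports only a ceiling equal to an unstated level.

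**The paragraph's example of a predictor is inflammatory markers, which are measured and not randomised.** The Introduction to the Revised Proposal also promises to relate changes in stress/anxiety to alcohol use. In such a model the first condition is not capped at α. This limits the bound to the models under Specific Analyses, which contain no measured predictor. It does not rescue the rule, because on any reading the gate holds no interaction test.

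**The rule is not exclusive.** It says that variables passing the screen will be explored. It does not say that others may not be, and post hoc analyses are allowed under FDR. This stands. A reader might infer that the trial will almost never look at moderators, but the documents show only that no other moderator route is planned.

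**No aim or hypothesis concerns moderation.** This stands. The Innovation section's remark about people whose AUD is stress-driven explains who is enrolled. It does not predict a varying effect within the sample.

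**Imbalance does little harm to the interaction estimate itself.** A reader might infer that the admitted variables give the least reliable interaction estimates. Simulation does not support that: the mean standard error was 0.315 in trials passing the arm screen against 0.299 otherwise (ratio 1.05), and 0.608 against 0.576 for a 50/50 binary factor (ratio 1.06).

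**Differential dropout** could raise imbalance among completers above α. That would select on attrition, which is still not moderation.

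**Conclusion.** The point holds as a defect in an exploratory rule. The only planned way of choosing moderators uses a screen that does not test effect modification. In the primary models, the chance that it admits a true moderator cannot exceed the screening level: about 5%, 10% or 20% at 0.05, 0.10 or 0.20. It is well below that when the characteristic has little average association with the outcome, and for an urn-balanced factor such as gender.

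The ceiling rests on randomisation, on reading the predictor as treatment arm, and on a screening test that holds its size. It does not depend on the assumed effect sizes; the simulated rates below the ceiling do, and they come from a single-outcome model without time or cold-pressor factors.

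No primary estimate or error rate changes through the moderator clause. A report that no moderators met criteria would say nothing about whether the effect is uniform, although the documents do not propose to draw that conclusion.

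**What to change.** Remove the moderator clause from the confounder sentence. In its place, before unblinding, fix a short list of moderators from data already collected, for example gender, AUDIT, baseline HAM-A, baseline PSS and the DMQ-R coping score. Add treatment × characteristic (× time, and × cold-pressor point in Aim 1) to the model whatever the balance between arms. Report estimates with intervals, labelled exploratory, under the FDR control already set for secondary analyses.

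The cost is one or two sentences and some extra model terms, with no new data. The downside is up to about 50 interaction tests, some of them four-way, with about 38% power for a 0.5 SD-per-SD moderator at N = 50 before FDR in the simplified model. The plan should therefore limit the list to key outcomes or report estimates only, and state that a null interaction is not evidence of a uniform effect.

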Exclusion criteria. Exhibit severe scores on the HAM-A, PSS, or PTSD checklist (PCL-5) – may be enrolled at the discretion of the admitting physician ([name]); physical dependence on alcohol (CIWAA > 10); greater than mild substance use disorder on drugs other than alcohol, nicotine, and marijuana; contraindications for taking pioglitazone; medical conditions (e.g., congestive heart failure, clinically significant edema, clinically significant liver disease, hypoglycemia, diabetes, history of bladder cancer) contraindicating pioglitazone pharmacotherapy or taking contraindicated medications (e.g., CYP2C8 inhibitors or inducers, antihyperglycemic medications); be pregnant, nursing, or planning on becoming pregnant during the course of the study; females will need to agree to use of barrier methods of contraception due to pioglitazone’s effects on plasma concentrations of oral contraceptives; have any other illness, condition, or use of medications, which in the opinion of the PI and/or admitting physician would preclude safe and/or successful completion of the study.

Baseline Screening. Participants will receive a comprehensive medical and psychiatric evaluation including a medical-history questionnaire, physical examination, laboratory chemistries (e.g., blood chemistry screen, complete blood count, urinalysis and serum pregnancy test), and ECG. Clinicians will conduct the **SCID**, the **ASI**⁶⁵, the **KMSK**⁶⁶ assessment of lifetime substance use interview, and **TLFB**⁶⁷. Alcohol dependence will be assessed using the SCID and the **CIWA-A**⁷⁴. A CIWA-A score > 10 will be exclusionary.

Alcohol-Related Measures. Assessment of alcohol use will include self-report (**TLFB**) and **BrAC** (Alco-Sensor FST, Intoximeters, Inc., Saint Louis, MO). The TLFB will be used to assessed the occurrence of heavy drinking days (>3 drinks/occasion for women>4 drinks/occasion for men)³⁵ in the past 7 days and average drinks/day for the past 7 days. Severity of alcohol use will be assessed using the **AUDIT**⁶⁹. **Alcohol craving** will be assessed using a 4-item questionnaire⁷⁵ during the stress reactivity assessment and the **PACS** at weekly clinic visits. Motivations for drinking will be assessed using the **DMQ-R**¹, with demonstrated utility in the general^{2,76,77} as well as clinical^{78,79} populations. The DMQ-R consists of 20 questions assessing motivations for drinking that are rated on a 1 “almost never/never” to 6 “almost always/always” scale. **ETG** will

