Inferential Paradigm Following recommendations in the literature¹⁰⁶⁻¹⁰⁸, analyses will utilize parallel frequentist and Bayesian statistical inference. Frequentist results yield the probability of the data (or data more extreme), given the null hypothesis, whereas Bayesian results directly yield the probability of an alternative hypothesis¹⁰⁹. If possible, Bayesian analyses will incorporate informative priors as they develop in the literature; otherwise, weakly informative priors will be incorporated as a default. Sensitivity analyses using optimistic and pessimistic, skeptical priors will evaluate prior assumptions¹¹⁰. Assessing the convergence of Bayesian analyses on the posterior distributions via Monte-Carlo Markov chain (MCMC) will use diagnostic evidence including effective sample size and scale reduction factors. Evaluation of posterior distributions will permit statements regarding the probability that effects of varying magnitudes exist, given the data. Statistical analyses will use the most up-to-date stable release version of the R statistical computing environment¹¹¹ using packages rstan¹¹¹ and brms¹¹².

Statistical Modeling Analyses will primarily use generalized linear modeling (GLM). Continuous, count, and dichotomous outcome variables will utilize normal, Poisson/negative binomial, and binomial distribution families respectively, with identity, log, and logit link functions as appropriate. Evaluation of distributional assumptions will use residual plots, formal statistical tests, and posterior predictive checking. Violations of assumptions will be addressed via transformation, robust estimation, stratification, and/or coefficient scaling where appropriate.

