HAM-A) compared to those receiving placebo. **Hypothesis 2b:** Participants receiving pioglitazone will show greater reductions in weekly psychometric measures of alcohol craving (primary measures: PACS) compared to those receiving placebo. **Hypothesis 2c:** Participants receiving pioglitazone will show greater reductions in past week alcohol use (primary measures: heavy drinking days as defined by >3 drinks/occasion for women and >4 drinks/occasion for men, average drinks/day) compared to those receiving placebo.

For all hypotheses, GLMM will model primary outcome measures as a function of the main effects and interaction between treatment and time.

Sample Size and Power Considerations

Frequentist Analyses. Power for **Specific Aim 1** is based on the rate at which we may detect the three-way interaction between time, treatment, and CPT measurement point for a given measure of stress reactivity (transformed for normality) across $k = 1000$ Monte Carlo simulations (executed via SAS 9.4). Calculations assume the following conditions: $\alpha = 0.05$, an autocorrelation of $r = 0.50$ between consecutive observations (with a decay of $r = -0.10$ for subsequent observations), and a small correlation of $r = 0.05$ for observations occurring at the same time point across groups. Based on these assumptions, the different sample sizes (pragmatic and pessimistic) stipulated in **Table 3** each provide power to detect small-to-moderate effect sizes (treatment group differences expressed as Cohen's D, with effects unfolding in linear fashion over time). Power for **Specific Aim 2** is based on evaluating reductions in drinks per week. Estimates are derived using G*Power 3.1.9.2. Assuming $\alpha = 0.05$ (two-tailed) and an average baseline of drinks/week across participants (calculated as an average from 14 and 7 drinks/week for a 3:1 ratio of males to females, respectively), the different sample sizes (pragmatic and pessimistic) stipulated in **Table 3** each provide power to detect varying decreases in alcohol consumption.

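### Heavy drinking days cannot exceed 7 per week, yet the family rule points them to Poisson/negative binomial, which can cost power and give the Bayesian analysis a poor likelihood; name a beta-binomial model

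*Combined protocol and SAP*

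**What the plan says.** Under Alcohol-Related Measures, the timeline followback (TLFB) gives heavy drinking days "in the past 7 days and average drinks/day for the past 7 days". Under Specific Analyses, Hypothesis 2c lists "primary measures: heavy drinking days as defined by >3 drinks/occasion for women and >4 drinks/occasion for men, average drinks/day". The Missingness & Multiple Comparisons paragraph says that primary outcomes "will be evaluated at the $\alpha = 0.05$ statistical significance level". The Aim 2 model is a mixed model with treatment, time and their interaction; no family is named there.

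The family comes from the Statistical Modeling paragraph: "Continuous, count, and dichotomous outcome variables will utilize normal, Poisson/negative binomial, and binomial distribution families respectively", "with identity, log, and logit link functions as appropriate". The paragraph then adds: "Evaluation of distributional assumptions will use residual plots, formal statistical tests, and posterior predictive checking". For violations it lists transformation, robust estimation, stratification and scaling of coefficients. It gives no rule for choosing among them and does not list a change of family. Heavy drinking days are not mentioned by name, and neither is the ceiling of 7.

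The Inferential Paradigm paragraph runs frequentist and Bayesian analyses in parallel, using rstan and brms. The Bayesian Analyses paragraph focuses on posterior probabilities of 0.75 or more.

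**The concern.** A weekly number of heavy days is a number out of 7. Under a binomial model its variance is 7p(1−p), which is below the mean 7p and shrinks as the mean approaches 7. The Poisson variance equals the mean, and the negative binomial variance is at least the mean. Neither can represent variance below the mean, so for binomial-like days the model-based standard errors are too large.

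What is at stake is power on a primary outcome in a trial of 25 completers per arm, together with the credibility of the Bayesian posterior, whose likelihood would allow weeks of 8 or more heavy days.

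**Working it through.** **Inputs.** From the documents: window of 7 days; alpha 0.05 (the Aim 2 power statement is two-tailed); 25 completers per group; weekly TLFB at Weeks 0 to 8, so 9 visits. Assumed: the mean and clustering of heavy days. The only heavy-drinking effect size given is a within-subject pilot Cohen's D of 0.8. The plan has no power or error-rate figure for this outcome to reproduce; the Aim 2 columns of Table 3 concern drinks per week.

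**Step 1: size when days are binomial-like.** With p = mean/7, the Poisson standard error is too large by 1/√(1−p). The actual two-sided level is 2Φ(−1.96/√(1−p)). The last column is a one-week simulation with 25 per arm.

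| Mean days | p | SE ratio | Actual level | Simulated, Poisson and NB |
|---|---|---|---|---|
| 2.1 | 0.30 | 1.195 | 0.019 | 0.02 |
| 3.5 | 0.50 | 1.414 | 0.006 | 0.004 |
| 4.9 | 0.70 | 1.826 | 0.0003 | 0.000 |

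**Step 2: power, one week, 25 per arm, binomial-like days.**

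- Fall from 3.5 to 2.8. The log rate ratio is 0.2231 in size. The Poisson SE is √(1/87.5 + 1/70) = 0.1604; the true SE is √(0.5/87.5 + 0.6/70) = 0.1195. Power = Φ((0.2231 − 1.96×0.1604)/0.1195) = Φ(−0.76) = 0.22. On the logit scale the effect is 0.4055 with SE √(1/(175×0.25) + 1/(175×0.24)) = 0.2160, so a binomial model has power Φ(1.88 − 1.96) = 0.47. Simulation gave 22% for Poisson and 43% for a beta-binomial.
- Fall from 4.9 to 4.2. The log rate ratio is 0.1542 in size. The Poisson SE is √(1/122.5 + 1/105) = 0.1330; the true SE is √(0.3/122.5 + 0.4/105) = 0.0791. Power = Φ((0.1542 − 0.2607)/0.0791) = Φ(−1.35) = 0.09. The logit effect is 0.4418 with SE √(1/(175×0.21) + 1/(175×0.24)) = 0.2259, giving Φ(1.956 − 1.96) = 0.50. Simulation gave 10% for Poisson and 50% for a beta-binomial.

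**Step 3: what clustering does.** With within-week correlation ρ (beta-binomial), the true variance divided by the Poisson variance is (1−p)(1+6ρ). The first factor comes from the bound and only makes the Poisson test conservative. The second comes from clustering and only makes it anti-conservative.

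- ρ = 0.5, mean 2.1: 0.7×4 = 2.8, level 2Φ(−1.96/√2.8) = 0.24. Simulated 0.24.
- ρ = 0.5, mean 3.5: 0.5×4 = 2, level 2Φ(−1.96/√2) = 0.17. Simulated 0.17.
- A plain binomial lacks the offsetting (1−p): at ρ = 0.8 its ratio is 5.8, level 2Φ(−1.96/√5.8) = 0.42. Simulated 42%.

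In the same kind of clustered data (ρ 0.2 to 0.8, means 2.1 and 3.5) the negative binomial rejected 1.0% to 5.6%. Poisson with robust errors rejected 3.9% to 5.8% across means 1.2 to 4.9 and ρ 0 to 0.8. A beta-binomial likelihood-ratio test rejected 3.8% to 6.2% in eight settings from pure binomial to strong clustering.

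**Step 4: closer to the planned model.** Treatment-by-time test under no effect, 25 per group, 9 visits, 600 runs per row (Monte Carlo error about ±0.018 at 0.05). The mixed models have a random intercept only; the robust column is a marginal Poisson fit with a bias-reduced sandwich.

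| Data | Mean | Poisson mixed | Binomial(7) mixed | Poisson, robust SE |
|---|---|---|---|---|
| Binomial | 1.2 | 0.023 | 0.042 | 0.057 |
| Binomial | 2.8 | 0.013 | 0.067 | 0.048 |
| Binomial | 4.3 | 0.000 | 0.047 | 0.057 |
| Beta-binomial, ρ 0.2 | 2.8 | 0.078 | 0.185 | 0.053 |
| Beta-binomial, ρ 0.5 | 2.8 | 0.213 | 0.360 | 0.068 |
| Random slopes, SD 1 | 2.9 | 0.092 | 0.185 | 0.058 |
| Random slopes, SD 2 | 2.9 | 0.182 | 0.338 | 0.038 |

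**Step 5: impossible weeks.** The Poisson probability of more than 7 days is 0.1% at mean 2, 2.7% at 3.5, 5.1% at 4 and 13.3% at 5.

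**The case against.** The plan never assigns heavy drinking days to a family by name. Treating them as a count is the natural reading, but still a reading. The same paragraph plans distributional checks, and a posterior predictive check would show weeks above 7 directly. It also lists robust estimation, which held test size between 3.8% and 6.8% in every setting tried. A reader might therefore infer too much from the wording in saying that the standard errors and error rate will be wrong. That objection stands: the documents support only that they can be wrong if model-based errors are used unchecked.

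A reader might also infer that the stated family inflates false positives. It does not as a whole. Inflation appears for plain Poisson, its cause is overdispersion rather than the bound, and the negative binomial half of the stated family or robust errors control it. A plain binomial out of 7 would be worse.

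A third tempting reading is that many weeks lie near 7 at entry. The documents do not show this. The weekly entry thresholds are above 7 and above 14 drinks, and the power baseline is (3×14 + 7)/4 = 12.25 drinks per week. If the mean is about 1 to 2 days, the bound costs little.

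Two things survive. First, the remedies come with no trigger or order, so the choice for a primary outcome would be made after seeing the data. Second, a sandwich correction does not change the likelihood from which the Bayesian posterior probabilities are read.

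**Conclusion.** The point holds as a specification gap with a real but conditional cost. Followed literally, the family rule gives this 0–7 primary outcome a model that cannot represent variance below the mean. For binomial-like days at moderate to high means, the model-based test is conservative, with power roughly halved at 3.5 to 2.8 days and cut to about a fifth at 4.9 to 4.2. This loses power and does not add false positives. Robust errors mend the frequentist size but not the Bayesian likelihood.

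The sizes rest on assumed means and dispersion. The power figures and the beta-binomial results are for a single week, not the nine-visit mixed model. It is a cheap improvement, not a flaw that invalidates the analysis.

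**What to change.** In Statistical Modeling, and again under Hypothesis 2c, name the model for heavy drinking days: beta-binomial, heavy days out of TLFB-covered days (normally 7), logit link, participant random effects, with the same family in the brms model. Do not use a plain binomial without the extra-variation term. State whether the random effects include a slope over time, since unmodelled slopes also inflated the random-intercept models in Step 4. If the Poisson/negative binomial family is kept for the frequentist test, specify robust errors in advance and still use a bounded likelihood for the Bayesian analysis.

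The cost is SAP wording only; no data collection changes. The downside is that the effect becomes an odds ratio, so the report should convert it to days per week.
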